11.5 Rescue Medications & Supportive Care

11.5.1 Supportive Care Guidelines

Subjects should receive appropriate supportive care measures as deemed necessary by the treating investigator. Suggested supportive care measures for the management of adverse events with potential immunologic etiology are outlined below. Where appropriate, these guidelines include the use of oral or intravenous treatment with corticosteroids as well as additional anti-inflammatory agents if symptoms do not improve with administration of corticosteroids. Note that several courses of steroid tapering may be necessary as symptoms may worsen when the steroid dose is decreased. For each disorder, attempts should be made to rule out other causes such as metastatic disease or bacterial or viral infection, which might require additional supportive care. The treatment guidelines are intended to be applied when the investigator determines the events to be related to pembrolizumab.

Note: if after the evaluation the event is determined not to be related, the investigator is instructed to follow the ECI reporting guidance (Section 20.7).

It may be necessary to perform conditional procedures such as bronchoscopy, endoscopy, or skin photography as part of evaluation of the event. Suggested conditional procedures, as appropriate, can be found in the ECI guidance document.

- **Pneumonitis:**

- For **Grade 2 events**, treat with systemic corticosteroids. When symptoms improve to Grade 1 or less, steroid taper should be started and continued over no less than 4 weeks.
- For **Grade 3-4 events**, immediately treat with intravenous steroids. Administer additional anti-inflammatory measures, as needed.
- Add prophylactic antibiotics for opportunistic infections in the case of prolonged steroid administration.

- **Diarrhea/Colitis:**

Subjects should be carefully monitored for signs and symptoms of enterocolitis (such as diarrhea, abdominal pain, blood or mucus in stool, with or without fever) and of bowel perforation (such as peritoneal signs and ileus).

- All subjects who experience diarrhea/colitis should be advised to drink liberal quantities of clear fluids. If sufficient oral fluid intake is not feasible, fluid and electrolytes should be substituted via IV infusion. For Grade 2 or higher diarrhea, consider GI consultation and endoscopy to confirm or rule out colitis.
 - For **Grade 2 diarrhea/colitis**, administer oral corticosteroids.
 - For **Grade 3 or 4 diarrhea/colitis** treat with intravenous steroids followed by high dose oral steroids.
 - When symptoms improve to Grade 1 or less, steroid taper should be started and continued over no less than 4 weeks.
- **Type 1 diabetes mellitus (if new onset, including diabetic ketoacidosis [DKA]) or ≥ Grade 3 Hyperglycemia, if associated with ketosis (ketonuria) or metabolic acidosis (DKA)**
 - For **T1DM** or **Grade 3-4 Hyperglycemia**
 - Insulin replacement therapy is recommended for Type I diabetes mellitus and for Grade 3-4 hyperglycemia associated with metabolic acidosis or ketonuria.
 - Evaluate patients with serum glucose and a metabolic panel, urine ketones, glycosylated hemoglobin, and C-peptide.
- **Hypophysitis:**
 - For **Grade 2** events, treat with corticosteroids. When symptoms improve to Grade 1 or less, steroid taper should be started and continued over no less than 4 weeks. Replacement of appropriate hormones may be required as the steroid dose is tapered.
 - For **Grade 3-4** events, treat with an initial dose of IV corticosteroids followed by oral corticosteroids. When symptoms improve to Grade 1 or less, steroid taper should be started and continued over no less than 4 weeks. Replacement of appropriate hormones may be required as the steroid dose is tapered.
- **Hyperthyroidism or Hypothyroidism:**

Thyroid disorders can occur at any time during treatment. Patients will be monitored for changes in thyroid function (at the start of treatment, periodically during treatment, and as indicated based on clinical evaluation) and for clinical signs and symptoms of thyroid disorders.

 - **Grade 2 hyperthyroidism events (and Grade 3-4 hypothyroidism):**
 - In hyperthyroidism, non-selective beta-blockers (e.g. propranolol) are suggested as initial therapy.

- In hypothyroidism, thyroid hormone replacement therapy, with levothyroxine or liothyronine, is indicated per standard of care.
 - **Grade 3-4** hyperthyroidism
 - Treat with an initial dose of IV corticosteroid followed by oral corticosteroids. When symptoms improve to Grade 1 or less, steroid taper should be started and continued over no less than 4 weeks. Replacement of appropriate hormones may be required as the steroid dose is tapered.
- **Hepatic:**
 - For **Grade 2** events, monitor liver function tests more frequently until returned to baseline values (consider weekly).
 - Treat with IV or oral corticosteroids
 - For **Grade 3-4** events, treat with intravenous corticosteroids for 24 to 48 hours.
 - When symptoms improve to Grade 1 or less, a steroid taper should be started and continued over no less than 4 weeks.
- **Renal Failure or Nephritis:**
 - For **Grade 2** events, treat with corticosteroids.
 - For **Grade 3-4** events, treat with systemic corticosteroids.
 - When symptoms improve to Grade 1 or less, steroid taper should be started and continued over no less than 4 weeks.
- **Management of Infusion Reactions:** Signs and symptoms usually develop during or shortly after drug infusion and generally resolve completely within 24 hours of completion of infusion.
Table 2 below shows treatment guidelines for subjects who experience an infusion reaction associated with administration of pembrolizumab (MK-3475).

Table 2 Infusion Reaction Treatment Guidelines

NCI CTCAE Grade	Treatment	Pre medication at subsequent dosing

Grade 1 Mild reaction; infusion interruption not indicated; intervention not indicated
	
Increase monitoring of vital signs as medically indicated until the subject is deemed medically stable in the opinion of the investigator.
	
None

Grade 2 Requires infusion interruption but responds promptly to symptomatic treatment (e.g., antihistamines, NSAIDS, narcotics, IV fluids); prophylactic medications indicated for <=24 hrs.
	
Stop Infusion and monitor symptoms. Additional appropriate medical therapy may include but is not limited to: IV fluids Antihistamines NSAIDS Acetaminophen Narcotics
 
Increase monitoring of vital signs as medically indicated until the subject is deemed medically stable in the opinion of the investigator.
 
If symptoms resolve within one hour of stopping drug infusion, the infusion may be restarted at 50% of the original infusion rate (e.g., from 100 mL/hr. to 50 mL/hr.). Otherwise dosing will be held until symptoms resolve and the subject should be pre-medicated for the next scheduled dose.
 
Subjects who develop Grade 2 toxicity despite adequate pre medication should be permanently discontinued from further trial treatment administration.
	
Subject may be pre-medicated 1.5h (\pm 30 minutes) prior to infusion of pembrolizumab (MK-3475) with:
 
Diphenhydramine 50 mg po (or equivalent dose of antihistamine).
 
Acetaminophen 500-1000 mg po (or equivalent dose of antipyretic).


Grades 3 or 4 Grade 3:
	
Stop Infusion.
	
No subsequent dosing

NCI CTCAE Grade	Treatment	Pre medication at subsequent dosing

Prolonged (i.e., not rapidly responsive to symptomatic medication and/or brief interruption of infusion); recurrence of symptoms following initial improvement; hospitalization indicated for other clinical sequelae (e.g., renal impairment, pulmonary infiltrates)
 
Grade 4: Life-threatening; pressor or ventilatory support indicated
	
Additional appropriate medical therapy may include but is not limited to:
 
 IV fluids Antihistamines NSAIDS Acetaminophen Narcotics Oxygen Pressors Corticosteroids Epinephrine 
Increase monitoring of vital signs as medically indicated until the subject is deemed medically stable in the opinion of the investigator.
 
Hospitalization may be indicated.
 
Subject is permanently discontinued from further trial treatment administration.
	

Appropriate resuscitation equipment should be available in the room and a physician readily available during the period of drug administration.
		

11.6 Dose Modifications for Obese Patients

There is no clearly documented adverse impact of treatment of obese patients. Pembrolizumab is being given at a set dose of 200 mg so body weight and/or obesity is not relevant to this study.

12.0 BLINDING

This is an open-label study; therefore, each patient will be aware of his or her own assigned treatment. All staff involved in treating and caring for study patients will have full knowledge of treatment assignments for those patients under their care.

13.0 CONCOMITANT THERAPY/VACCINATIONS

Medications or vaccinations specifically prohibited in the exclusion criteria are not allowed during the ongoing trial. If there is a clinical indication for one of these or other medications or vaccinations specifically prohibited during the trial, discontinuation from trial therapy or vaccination may be required. The investigator should discuss any questions regarding this with the Merck Clinical team. The final decision on any supportive therapy or vaccination rests with the investigator and/or the subject's primary physician. Any disease progression requiring other forms of specific anti-tumor therapy will be cause for early discontinuation of study therapy. Acceptable and prohibited concomitant therapies are reviewed below.

13.1 Acceptable Concomitant Medications

All treatments that the investigator considers necessary for a subject's welfare may be administered at the discretion of the investigator in keeping with the community standards of medical care. All concomitant medication will be recorded on the case report form (CRF) including all prescription, over-the-counter (OTC), herbal supplements, and IV medications and fluids. If changes occur during the trial period, documentation of drug dosage, frequency, route, and date may also be included on the CRF.

All concomitant medications received within 30 days before the first dose of trial treatment and 30 days after the last dose of trial treatment should be recorded. Concomitant medications administered after 30 days after the last dose of trial treatment should be recorded for SAEs and ECIs as defined in Section 20.5.

13.2 Prohibited Concomitant Medications

Subjects are prohibited from receiving the following therapies during the Screening and Treatment Phase of this trial:

- Antineoplastic systemic chemotherapy or biological therapy
- Immunotherapy not specified in this protocol
- Chemotherapy not specified in this protocol
- Investigational agents other than pembrolizumab
- Radiation therapy other than post-operative radiation for lung cancer
- Live vaccines within 30 days prior to the first dose of trial treatment and while participating in the trial. Examples of live vaccines include, but are not limited to, the following: measles, mumps, rubella, varicella/zoster, yellow fever, rabies, BCG, and typhoid vaccine.
- Systemic glucocorticoids for any purpose other than to modulate symptoms from an event of clinical interest of suspected immunologic etiology. The use of physiologic doses of corticosteroids may be approved after consultation with the Sponsor.

Subjects who, in the assessment by the investigator, require the use of any of the aforementioned treatments for clinical management should be removed from the trial. Subjects may receive other medications that the investigator deems to be medically necessary.

The Exclusion Criteria describes other medications which are prohibited in this trial. There are no prohibited therapies during the Post-Treatment Follow-up Phase.

14.0 DIET/ACTIVITY/OTHER CONSIDERATIONS

14.1 Diet

Subjects should maintain a normal diet unless modifications are required to manage an AE such as diarrhea, nausea or vomiting.

14.2 Contraception

Pembrolizumab may have adverse effects on a fetus in utero. Furthermore, it is not known if pembrolizumab has transient adverse effects on the composition of sperm. Non-pregnant, non-breast-feeding women may be enrolled if they are willing to use 2 methods of birth control or are considered highly unlikely to conceive. Highly unlikely to conceive is defined as 1) surgically sterilized, or 2) postmenopausal (a woman who is ≥ 45 years of age and has not had menses for greater than 1 year will be considered postmenopausal). The two birth control methods can be either two barrier methods or a barrier method plus a hormonal method to prevent pregnancy. Subjects should start using birth control from study Visit 1 throughout the study period up to 120 days after the last dose of study therapy.

The following are considered adequate barrier methods of contraception: diaphragm, condom (by the partner), copper intrauterine device, sponge, or spermicide. Appropriate hormonal contraceptives will include any registered and marketed contraceptive agent that contains an estrogen and/or a progestational agent (including oral, subcutaneous, intrauterine, or intramuscular agents).

Subjects should be informed that taking the study medication may involve unknown risks to the fetus (unborn baby) if pregnancy were to occur during the study. In order to participate in the study, they must adhere to the contraception requirement (described above) for the duration of the study and during the follow-up period defined in section 20.4 -Reporting of Pregnancy and Lactation to the Sponsor and to Merck. If there is any question that a subject will not reliably comply with the requirements for contraception, that subject should not be entered into the study.

14.3 Use in Pregnancy

If a subject inadvertently becomes pregnant while on treatment with pembrolizumab, the subject will immediately be removed from the study. The site will contact the subject at least monthly and document the subject's status until the pregnancy has been completed or terminated. The outcome of the pregnancy will be reported to the Sponsor and to Merck without delay and within 24 hours to the Sponsor and within 2 working days to Merck if the outcome is a serious adverse experience (e.g., death, abortion, congenital anomaly, or other disabling or life-threatening complication to the mother or newborn).

The study investigator will make every effort to obtain permission to follow the outcome of the pregnancy and report the condition of the fetus or newborn to the Sponsor. If a male subject impregnates his female partner the study personnel at the site must be informed immediately and the pregnancy reported to the Sponsor and to Merck and followed as described above and in Section 20.4.

14.4 Use in Nursing Women

It is unknown whether pembrolizumab is excreted in human milk. Since many drugs are excreted in human milk, and because of the potential for serious adverse reactions in the nursing infant, subjects who are breast-feeding are not eligible for enrollment.

15.0 TREATMENT COMPLIANCE

Deviation(s) from the prescribed dosage regimen are to be recorded in the comments section of the CRF.

15.1 Subject Withdrawal/Discontinuation Criteria

The End of Treatment and Follow-up visit procedures are listed in Appendix A (Study Schedule) and Section 9.0 (Study Periods-Visit Requirements). After the end of treatment, each subject will be followed for 30 days for adverse event monitoring (serious adverse events will be collected for 90 days after the end of treatment (Section 20.5.1). Subjects who discontinue for reasons other than progressive disease will have post-treatment follow-up for disease status until disease progression, initiating a non-study cancer treatment, withdrawing consent or becoming lost to follow-up. For all other subject's outcome data will be collected for 2 years, then every 6 months for up to five years. Every effort should be made to collect information regarding disease during this follow-up which may include the start of new anti-neoplastic therapy, disease progression, death, or end of study. When a subject discontinues/withdraws prior to trial completion, all applicable activities scheduled for the final trial visit should be performed at the time of discontinuation. Any adverse events which are present at the time of discontinuation/withdrawal should be followed in accordance with the safety requirements outlined in Section 9.8.5& 20. .

A subject must be discontinued from the trial for any of the following reasons:

- The subject or legal representative (such as a parent or legal guardian) withdraws consent.

- Confirmed radiographic disease progression

Note: For unconfirmed radiographic disease progression, please see Section 17.3.1. A subject with evidence of possible target lesion growth or new lesion appearance will not be presumed to have progressed and will proceed to surgery as long as all possible site(s) of disease are deemed resectable by the surgeon.

- There is toxicity deemed by the investigator or subject to be unacceptable
- Concurrent illness that prevents further administration of treatment
- Investigator's decision to withdraw the subject
- The subject has a confirmed positive serum pregnancy test
- Noncompliance with trial treatment or procedure requirements
- The subject is lost to follow-up
- Administrative reasons
- The investigator, for any reason, stops the study
- Termination of the study by Merck
- The patient, for any reason, requires treatment with another systemic agent potentially effective for treatment of the study indication. In this case, discontinuation from the study occurs immediately upon introduction of the new agent.
- A patient who cannot be administered the study drug after a 21-day delay must be discontinued from the study treatment.
- A patient with bulky residual adenopathy such that resection is not attempted will be removed from protocol therapy and should receive standard oncology care as deemed appropriate by the treating physician.
- The compulsory detention for the treatment of either a psychiatric or physical (e.g. infections disease) illness.
- There is clear evidence of progressive disease.

In previous studies with pembrolizumab in solid tumors there has been transient increase in lesion size due to inflammatory immune response followed by clear evidence of lesion regression. Therefore, CAT scan evidence of progression in the global tumor burden will not be criteria for discontinuation or by itself deemed evidence of progression on therapy. It is possible index tumor may enlarge > 25% or new lesions appear after 2 doses pembrolizumab before repeat CAT scan. Surgical staging at time of resection will verify progression or whether robust inflammatory response was misinterpreted as progression on repeat CAT scans.

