4.0 OBJECTIVES

4.1 Primary objective

The primary objective of the single arm phase II trial is to determine whether the surgery feasibility rate of neoadjuvant pembrolizumab is not significantly worse than the historical surgical feasibility rate of neoadjuvant chemotherapy. Surgery feasibility rate of a neoadjuvant therapy is the percent of

20

The information contained in this document is regarded as confidential, and may not be disclosed to another party unless such disclosure is required to initiate the study, to conduct study-related activities, or to comply with national, state, or local laws and regulations. Written authorization from the coordinating site and sponsor is required for disclosure otherwise.

11 Nov 2018

patients who are able to undertake surgery after the neoadjuvant therapy. A total of 30 eligible patients will be registered to the single arm trial. Taking 5% rate of cancellation and ineligibility into account, the trial will enroll a total of 32 patients and eligible subjects (not screen failures) will be followed for 2 years for both disease recurrence and death.

Primary Objective Sample Size Justification

According to Pisters et al (JCO 2010), approximately 80% of subjects undergo surgical exploration within 42 days of day 1 of the last cycle of standard neoadjuvant chemotherapy. We would like to test the following hypotheses:

$$H_0: p \geq 0.80 \text{ vs. } H_a: p < 0.65$$

where p is the true surgery feasibility rates after neoadjuvant pembrolizumab. With 30 evaluable patients receiving protocol treatment, the study has approximately 84.6% power rejecting $H_0: p \geq 0.80$ when $p=0.65$ at one-sided significance level of 15%.

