5.0 STUDY PLAN /DESIGN

Standard diagnostic and staging work up will be performed prior to or during surgery according to institutional standard practice including: pathologic/histologic diagnosis of non-small cell lung cancer, PET/CT scan, brain imaging, and if clinically indicated, mediastinoscopy. Two doses of neoadjuvant pembrolizumab will be given. Standard surgical evaluation and surgery will be performed following completion of 2 cycles of neoadjuvant pembrolizumab therapy.

After surgery, patients who are appropriate candidates will receive adjuvant chemotherapy, adjuvant radiation, and follow-up as per standard of care and institutional best practice. After all standard therapy, patients will receive 4 additional cycles of pembrolizumab every 21 days for 4 cycles. Patients who are not candidates for adjuvant therapy or who refuse may receive four cycles of adjuvant pembrolizumab.

All post-surgical therapy is as per institutional standard of care and is not study specific. Post-surgery chemotherapy, radiation may be given through the patient's primary oncology team as per the wishes of the patient. This allows a patient to have neoadjuvant pembrolizumab and surgery at an institution participating in this study, receive standard chemotherapy and radiation therapy near home, and return to the institution participating in the study to receive adjuvant pembrolizumab. Patients will be seen for a visit approximately 30 days after the last dose of pembrolizumab and follow-up will continue until pembrolizumab related side effects are grade 1, or Investigator deems stable. Patients will be followed for outcome for up to 7 years. Long term outcome data may be collected by phone.

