19.3.3 Subsequent Anti-Cancer Therapy Status

The investigator or qualified designee will review all new anti-neoplastic therapy initiated after the last dose of trial treatment. If a subject initiates a new anti-cancer therapy within 30 days after the last dose of trial treatment, the 30-day Safety Follow-up visit must occur before the first dose of the

new therapy. Once new anti-cancer therapy has been initiated the subject will move into survival follow-up.

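### Section 15.1 ends disease-status follow-up when a patient who left protocol therapy without progression starts a non-study cancer treatment, while 4.1, 5.0, 9.8.6 and 27.1 follow patients for recurrence or outcome with no such exception

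*Combined protocol and SAP*

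**What the plan says.** **The stop rule.** Section 15.1 says: "Subjects who discontinue for reasons other than progressive disease will have post-treatment follow-up for disease status until disease progression, initiating a non-study cancer treatment"; withdrawal of consent and loss to follow-up also end it. The next sentence covers all other subjects, for whom "outcome data will be collected for 2 years, then every 6 months for up to five years". Section 19.3.3 adds: "Once new anti-cancer therapy has been initiated the subject will move into survival follow-up". It does not mention recurrence.

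**The general rule.** Section 4.1, repeated in the 27.1 overview, says "eligible subjects (not screen failures) will be followed for 2 years for both disease recurrence and death". Section 5.0 says "Patients will be followed for outcome for up to 7 years". Section 9.8.6 collects recurrence and survival every 3-4 months for two years after surgery, then six-monthly up to five years, and allows collection by phone. Section 27.1, under accrual and follow-up, commits to following every registered patient for DFS and overall survival. None of these carves out patients who start new therapy.

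**The endpoint.** Sections 4.2, 17.6 and 27.1 define DFS as surgery to first recurrence or death. It is estimated by Kaplan-Meier, with the median as the named statistic. No section gives a censoring rule or says how new anti-cancer therapy is handled.

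**The concern.** Two follow-up rules in one protocol give different instructions for the same patient: one who was resected, stopped protocol therapy without progression (for toxicity, say) and then started another cancer treatment before any recurrence. Under 15.1 and 19.3.3 the site stops collecting disease status and records survival only. Under 4.1, 9.8.6 and 27.1 it goes on collecting recurrence.

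If sites follow 15.1, recurrence dates in these patients are never collected, and no later analysis can restore them. The gap would depend on why the patient changed treatment, so censoring in the Kaplan-Meier estimate could be informative. DFS also feeds the Cox models in secondary objective 3. In a multi-institution trial, different sites could follow different rules.

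**Working it through.** The plan states no DFS rate, number of switchers or censoring rule, so there is no figure to reproduce. The conflict is textual. The arithmetic below only gauges its size.

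**Inputs from the documents.** 30 evaluable patients, with surgery feasibility of 80% (null) or 65% (alternative). DFS covers resected patients only: 30 × 0.80 = 24, or 30 × 0.65 = 19.5, about 20.

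**Assumed inputs, not in the documents.** Exponential DFS with a two-year rate of 75% in patients who do not switch; 5 of 24 switch at 6 months (2 of 24 as a lower case); hazard ratio (HR) of switchers to the rest of 2 or 3; 10% of first events are deaths; median survival after recurrence 12 months; 60 months of follow-up.

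**Step 1: the mechanism, if every later event were lost.** With f the fraction switching at month 6:

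- S0(t) = 0.75^(t/24), so S0(6) = 0.9306.
- True S(t) = (1 − f)·S0(t) + f·S0(t)^HR.
- Kaplan-Meier limit at 24 months = S(6) × S0(24)/S0(6).

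For f = 5/24 and HR 2: S(24) = 0.7917 × 0.75 + 0.2083 × 0.5625 = 0.711; S(6) = 0.7917 × 0.9306 + 0.2083 × 0.8660 = 0.917; limit = 0.917 × 0.75/0.9306 = 0.739.

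| Switchers | HR | True | Kaplan-Meier | Difference (points) |
|---|---|---|---|---|
| 5/24 | 2 | 0.711 | 0.739 | +2.8 |
| 5/24 | 3 | 0.682 | 0.729 | +4.7 |
| 2/24 | 2 | 0.734 | 0.746 | +1.1 |
| 2/24 | 3 | 0.723 | 0.742 | +1.9 |
| any | 1 | 0.750 | 0.750 | 0 |

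For 5/24 and HR 0.7 the difference is about −1 point. These rows discard deaths, which 19.3.3 does not, so they show the mechanism and are not the estimate.

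**Step 2: the relevant case, deaths captured and recurrences lost.** Simulation, n = 24, 5 switchers. The result depends on how switchers with no recorded death are treated.

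| Switchers with no recorded death | HR 2 | HR 3 |
|---|---|---|
| Censored at start of new treatment | +1.9 | +3.2 |
| Kept at risk to last contact | +3.4 | +4.2 |

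So 24-month DFS is overstated by about 2 to 4 points.

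**Step 3: the median.** For 5/24 and HR 2, the median is unreached by 60 months in about 20% of simulated trials with full follow-up. With deaths captured it is unreached in about 22% (censored at the switch) to 28% (kept at risk).

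**Step 4: against sampling error.** The standard error of a 70% two-year rate is √(0.70 × 0.30/24) = 9.4 points, or √(0.21/20) = 10.2 points for n = 20. All the differences above are smaller than one standard error.

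**The case against.** **A workable reading exists.** Section 15.1 opens by referring to Appendix A and Section 9.0 for follow-up. Both collect recurrence and survival; in Appendix A note T, new therapy ends only toxicity follow-up. Section 15.1 also says "Every effort should be made to collect information regarding disease during this follow-up which may include the start of new anti-neoplastic therapy", which presumes that some patients stay in follow-up after starting new therapy. Sites that give weight to 27.1 would lose nothing. This stands as a reason to rate the point low. It does not remove the conflict: no text gives 27.1 precedence, and the request for every effort applies within a follow-up that the stop rule has already ended for these patients.

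**Few patients qualify.** This also stands. Standard adjuvant chemotherapy and radiation are part of the plan (3.1, 9.7, 9.8, 11.1), and treatment started because of recurrence comes after the DFS event. The 5 of 24 has no source in the documents.

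**Stronger readings that the documents do not support:**

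- *Patients with N2 disease or positive margins all drop out of follow-up.* Section 9.6 removes them from protocol, but they lose recurrence follow-up only if that removal overrides the schema, 9.8 and 11.1; if their post-operative therapy counts as non-study, which 3.1, 11.1 and 13.2 speak against; and if 15.1 overrides 4.1 and 27.1.
- *Section 13.2 is a further stop rule.* It says that patients who "require the use of any of the aforementioned treatments for clinical management should be removed from the trial", but its list applies during screening and treatment, and the section ends by stating that no therapy is prohibited in post-treatment follow-up.
- *Needing another systemic agent ends all data collection.* The 15.1 list says "In this case, discontinuation from the study occurs immediately upon introduction of the new agent". The same list discontinues patients for toxicity or concurrent illness, and 15.1 prescribes follow-up after discontinuation.
- *All later events are lost.* Section 19.3.3 keeps survival follow-up, so deaths are still recorded.
- *DFS must be biased upward.* If switchers are censored when they switch, the direction depends on their prognosis. If they are kept at risk, missed recurrences can only delay or remove events, which pushes DFS up. The plan does not say which applies.

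**Conclusion.** The contradiction is real and the point holds, as a minor one to consider. Sections 15.1 and 19.3.3, followed as written, would leave recurrences uncollected that the DFS analysis in 27.1 needs. The loss is confined to resected patients who leave protocol therapy and start other treatment before recurrence.

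If 5 of 24 switch at 6 months, the HR is 2 to 3 and deaths are captured, 24-month DFS is overstated by about 2 to 4 points; at HR 2 the median is unreached in about 22-28% of trials instead of about 20%. The bias shrinks toward zero with fewer switchers and vanishes if sites follow 4.1 and 27.1. DFS is secondary and declared exploratory, and the primary endpoint, surgery feasibility, is not affected.

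**What to change.** - **15.1, follow-up paragraph:** delete the start of a non-study cancer treatment as a stop for disease-status follow-up. State that all eligible subjects, including those who discontinue protocol therapy or start new anti-cancer therapy, are followed for recurrence and survival on the 9.8.6 schedule unless they withdraw consent or are lost to follow-up.
- **15.1, the item on needing another systemic agent only:** make the discontinuation one from study treatment. Leave the consent-withdrawal, loss-to-follow-up and study-termination items unchanged.
- **19.3.3:** name both recurrence and survival as the follow-up after new therapy.
- **27.1:** state that DFS uses recurrences and deaths observed after new therapy, with censoring at new therapy as an optional sensitivity analysis.

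The cost is an amendment to wording, a few more follow-up contacts (9.8.6 already allows phone collection) and possibly a less favourable DFS estimate.
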